#### Neurologic Acute Toxicity

If the number of patients with neurologic acute toxicity equals or exceeds the number in the table, then termination will be considered as it is likely that the toxicity rate is >10%, as noted by the Bayesian posterior probabilities.

Bayesian Rule for Neur	ologic Acu	te Toxicity	7			
Patients treated	1	2	3	4		
	5	5	5	5		
Patients who experience acute toxicity	3	5	6	7		
Posterior Prob[toxicity rate >10%]	0	0	0	0		
7 10/0]	6	8	7	7		
	8	2	9	7		
Action	T	Terminate enrollment				

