#### 7.1.3 Rules for Early Termination

Bayesian probability calculations will be employed to define rules of early termination for feasibility and safety. The tables below indicate termination rules after groups of 3 patients have been treated, although the Bayesian probability of an event may be calculated at any time during the trial. Hundreds of patients with certain types of cancer have undergone radiation therapy with protons. Thus, we will assume a modest amount of "prior" feasibility and safety data for proton for our Bayesian calculations. We will assume prior information equivalent to that of 6 treated patients, which is commonly required to establish safety in a standard 3+3 Phase-I trial design.

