#### Neurologic Acute Toxicity

Because radiation therapy is directed to the craniospinal axis, a neurologic acute toxicity rate  $\leq 10\%$  is considered acceptable. We will assume a beta (1,5) prior, which is information equivalent to acute neurologic toxicity in one of 6 treated patients. If the number of patients with neurologic acute toxicity equals or exceeds the number in the table, then termination will be considered as it is likely that the toxicity rate is  $\geq 10\%$ , as noted by the Bayesian posterior probabilities.

Bayesian Rule for Neurologic Acute Toxicity					
Patients treated 3 6 9 1					
				2	

Patients who experience acute toxicity	1	1	2	2	
Posterior Prob[toxicity rate	0	0	0	0	
>10%]		7	Q	. 7	
	1	0	4	6	
Action	To	erminate e	nrollment		

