### 7.1.4 Statistical Analyses

Feasibility. The initial target sample size of 12 patients will be revised to 12 additional base of skull patients to be treated with pencil beam protons and evaluated for feasibility by the new definition. It is anticipated that up to 5 additional spine patients may be enrolled. So the total enrollment after this amendment will be up to 17 patients (12 base of skull and 5 spine). The statistical analysis will calculate the posterior probability that the feasibility rate is >90%. This analysis will be conducted 2 ways: based on all 26 patients treated and on all 17 patients treated after the modification. The definition of infeasibility will be that which was current when the patient enrolled on the trial. There will be no retroactive re-grading of infeasibility in the base of skull patients.

Acute Toxicity. All toxicities observed within 90 days from start of therapy will be graded by CTC Version 4.0 and tabulated. Special attention is paid to neurologic toxicity.

Late Toxicity. All toxicities observed later than 90 days from start of therapy will be graded by the CTCAE version 4.0 and tabulated.

Progression-free and overall survival will be estimated by the survival analysis methods. It is most likely that these time-to-event outcomes will be summarized as part of the phase II study.

Fatigue is scored on a 10-point scale based on the Brief Fatigue Inventory Questionnaire. At each time point, the BFI score will be summarized by mean and standard deviation, and plotted over time. We will examine the plots for the expected worsening of function in the 6-12 months post-radiation and gradual improvement from 12-24 months. The fatigue scores will be summarized in detail in the phase II study.

Neurocognitive function (FACT-Br) will be summarized by descriptive statistics and scatter plots. It is most likely that the neurologic outcomes will be summarized as part of the phase II study.

Estimation of Event Rates. The table below displays the 90% exact binomial confidence

intervals based on 12 patients treated.

intervals ous	ed on 12 patients	i catea.			
No. of	%	90%	No. of	%	90%
Events		exact	Events		exact
		CI			CI
0	0.0	17.5*	7	58.3	31.5,
					81.9
1	8.3	.43,	8	66.7	39.1,
		33.9			87.7
2	16.7	3.0,	9	75.0	47.2,
		43.8			92.8
3	25.0	7.2,	10	83.3	56.1,
		52.7			97.0
4	33.3	12.3,	11	91.7	66.1,
		60.9			99.6
5	41.7	18.1,	12	100.0	82.5*
		68.5			

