#### 7.2.1 Design and Objectives.

Proton therapy at standard doses is not expected to improve clinical outcome but will likely reduce fatigue and toxicity. The purpose of the phase II study is to characterize toxicity rates and to summarize fatigue scores at time points during and post-radiation. Progression-free survival will also be estimated. There will be no early stopping in this phase of the study. Outcomes from the initial 12 patients will be included in this evaluation. An additional 38 patients will be enrolled on the phase II study, for a phase II study total of 50 patients. We may have to screen/enroll up to 50 subjects to reach the goal of 38 additional patients in the phase II portion of the trial.

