### 7.2.3 Rules for Early Termination; continuation of rules as in 7.1.3

#### Non-Neurologic Acute Toxicity

If the number of patients with non-neurologic acute toxicity equals or exceeds the number in the table, then termination will be considered as it is likely that the toxicity rate is >20%, as noted by the Bayesian posterior probabilities.

Bayesian Rule for Non-Neurol	logic A	Acute Toxicit	У	
Patients treated	1	2	3	4

Version: 04/04/2014

Patients who experience acute toxicity Posterior Prob[toxicity rate >20%]	5 5 0	5 7 0	5 9 0	5 1 1 0
2070]	8	7	7	7
Action	0   T	6 Cerminate e	nrollment	1

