#### 7.3 SAMPLE SIZE/POWER AND TRIAL DURATION.

Twelve evaluable patients will be enrolled on the feasibility portion of the trial. We estimate having to screen/enroll 18 subjects to reach the goal of 12 evaluable subjects. If feasibility and safety are acceptable, then an additional 38 patients will be enrolled for a study total of 50 patients. We may have to screen/enroll up to 50 subjects to have an additional 38 patients participate in the phase II portion of the trial. We estimate that the first 12 patients will be enrolled in 1 year. Then the study will be suspended for patient observation for 2 months for feasibility and safety evaluation. If the feasibility study is acceptable, then accrual will continue. With an accrual of 12 patients per year, the study should be actively enrolling for 4 years. To test whether the 12 month rate of severe fatigue is lower than 50%, a one sample test will be performed. With 50 patients, there is 79% power to detect a 33% rate versus a null rate of 50% by chi-square test at 1-sided 5% significance.

For the feasibility study, the initial target sample size of 12 patients will be revised to 12 additional base of skull patients to be treated with pencil beam protons and evaluated for feasibility by the new definition. There will not be a target sample size for spine patients and we will enroll those patients while filling the enrollment goal for the base of skull patients. It is anticipated that up to 5 spine patients may be enrolled. The total enrollment to the feasibility study after this amendment will be up to 17 patients (12 base of skull and 5 spine).

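### In the Phase II neurologic-toxicity stopping table the counts and the posterior probabilities differ by one event in all four columns, and Section 7.2.1 says this phase has no early stopping

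*Combined protocol and SAP*

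**What the plan says.** Section 7.1.3 sets up the neurologic rule for the feasibility phase. A rate up to 10% is acceptable, and the prior is given as "We will assume a beta (1,5) prior, which is information equivalent to acute neurologic toxicity in one of 6 treated patients". It adds that "the Bayesian probability of an event may be calculated at any time during the trial". The Phase II section is headed "Rules for Early Termination; continuation of rules as in 7.1.3" and states no other prior.

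The Phase II neurologic table in Section 7.2.3 is triggered when the number of patients with toxicity reaches or passes the tabulated count; "then termination will be considered as it is likely that the toxicity rate is >10%, as noted by the Bayesian posterior probabilities". Its entries are:

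| Patients treated | 15 | 25 | 35 | 45 |
|---|---|---|---|---|
| Boundary count | 3 | 5 | 6 | 7 |
| Printed P(rate > 10%) | 0.68 | 0.82 | 0.79 | 0.77 |

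The action row ends enrolment. Section 8.4 also refers the reader to Section 7 for stopping rules covering both phases. Section 7.2.1, on the same phase, says: "There will be no early stopping in this phase of the study".

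The feasibility enrolment was later enlarged. Section 7.3 says "The total enrollment to the feasibility study after this amendment will be up to 17 patients (12 base of skull and 5 spine"), and Section 7.1.4 plans an analysis "based on all 26 patients treated and on all 17 patients treated after the modification".

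**The concern.** The rule fires at the tabulated count or above, so the probability under a count should be the posterior at that count. In this table it is not. A reader cannot tell whether the counts are one too high for the intended level of evidence or the probabilities understate the evidence at the intended counts.

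At 2/15, 4/25, 5/35 or 6/45 the probability row describes the evidence as the boundary, while the count row says to continue. Anyone who recalculates the posterior at 3/15, as Section 7.1.3 permits, gets 0.87 and not the printed 0.68. Section 7.2.1 goes further and denies that this phase has any early stopping. This is the acute neurologic safety trigger in a trial that irradiates the skull base and spine.

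**Working it through.** **Inputs.** Prior Beta(1,5) and 10% threshold (Section 7.1.3, neurologic rule; carried forward by the heading of Section 7.2.3). Looks, counts and printed probabilities from the Section 7.2.3 table.

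**Formula.** With x events in n patients the posterior is Beta(1+x, 5+n−x), so P(rate > 0.10) = 1 − BetaCDF(0.10; 1+x, 5+n−x). This equals P(Bin(n+5, 0.10) ≤ x), which gives an independent check. For 3/15, P(Bin(20, 0.10) ≤ 3) = 0.867.

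**Controls: do the plan's other toxicity tables reproduce?**

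| Table | Counts | Recomputed posterior |
|---|---|---|
| Feasibility, neurologic (> 10%) | 1/3, 1/6, 2/9, 2/12 | 0.81, 0.70, 0.84, 0.76 |
| Feasibility, non-neurologic (> 20%) | 2/3, 2/6, 3/9, 4/12 | 0.80, 0.62, 0.70, 0.76 |
| Phase II, non-neurologic (> 20%) | 5/15, 7/25, 9/35, 11/45 | 0.80, 0.76, 0.73, 0.71 |

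All 12 agree with the print on every legible digit. One digit is unreadable in the text used here for each of 1/3, 2/9 and 9/35. The plan's convention is therefore the posterior evaluated at the printed count.

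**The Phase II neurologic table.**

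| n | Printed count | Printed probability | Posterior at printed count | Posterior at one event fewer |
|---|---|---|---|---|
| 15 | 3 | 0.68 | 0.867 | 0.677 (2/15) |
| 25 | 5 | 0.82 | 0.927 | 0.8245 (4/25) |
| 35 | 6 | 0.79 | 0.900 | 0.794 (5/35) |
| 45 | 7 | 0.77 | 0.878 | 0.770 (6/45) |

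At the printed counts every column is off by 0.11 to 0.19. At one event fewer, every column matches to two decimals.

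**Could another prior explain it?** About a dozen were tried. Only the limit Beta(0,6) reproduces the printed row at the printed counts. It must do so, because Beta(0+x, 6+n−x) is the same distribution as Beta(1+(x−1), 5+n−(x−1)). It would contradict the stated prior.

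**Consequence.** Exact binomial recursion, treating the boundary as a stop. The feasibility bounds are 1, 1, 2, 2 at 3, 6, 9, 12 patients. The Phase II bounds are 3, 5, 6, 7 as printed, against 2, 4, 5, 6 to match the probabilities.

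| Chance of reaching a boundary (printed counts vs matching counts) | True rate 10% | 15% | 20% |
|---|---|---|---|
| (a) Looks at 15 to 45, given the first 12 passed | 8.8% vs 26.0% | 33.3% vs 57.0% | 63.1% vs 81.4% |
| (b) All eight looks, 3 to 45 | 57.1% vs 65.2% | 80.5% vs 87.4% | 93.7% vs 96.8% |
| (c) Looks at 35 and 45 only | 18.5% vs 34.0% | 55.5% vs 72.3% | 84.0% vs 92.4% |

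Most of (b) comes from the feasibility rule, which alone triggers in 52.9%, 70.7% and 82.8%. The results in (a) follow from these by (all looks − feasibility)/(1 − feasibility); at 10%, (57.06 − 52.93)/(100 − 52.93) = 8.8%. Scenario (c) assumes 26 patients are treated before Phase II begins, so the looks at 15 and 25 have passed, and does not condition on earlier looks.

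**The case against.** The strongest reply is that the count row governs. The text ties the action to the number of patients, and the probabilities only explain it. Read literally, 2/15 does not reach the boundary, and either 0.68 or 0.87 supports calling a rate above 10% likely. If the probability row is the slip, the rule behaves as intended. Termination is only to be considered, and the Medical Monitor (Section 8.5) may recommend suspension whatever the table says. On early stopping, one sentence in Section 7.2.1 stands against a heading, two tables and Section 8.4. The size of the effect depends on the enrolment scenario, and across all eight looks the gap is only 3 to 8 percentage points.

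Much of this is fair. The literal trigger is the count, the rule is advisory, and the weight of the text suggests that Phase II rules are meant to exist. But none of it says whether the printed counts are the intended ones. With no stated cutoff, the probability row is the only record of how much evidence was meant to prompt action. The recomputed posteriors at the printed counts (0.87 to 0.93) lie above the whole range of the other 12 cells (0.62 to 0.84), while those at one event fewer (0.68 to 0.82) lie inside it. That is suggestive, not proof. Independent oversight does not repair a table that its users will consult, and the sentence in Section 7.2.1 remains a flat contradiction.

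**Conclusion.** The concern holds. The two rows of the Phase II neurologic table cannot both be right under the stated prior; they differ by exactly one event in all four columns. Four matches to two decimals rule out a text-extraction accident, and the controls rule out a misread method. The documents do not show which row is in error.

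At an acceptable 10% rate the choice moves the chance of reaching a Phase II boundary from 8.8% to 26.0% given a passed feasibility phase, from 18.5% to 34.0% if only the looks at 35 and 45 remain, and from 57.1% to 65.2% over all eight looks. These figures treat an advisory boundary as a firm stop. Scenarios (a) and (b) follow the plan for a first group of 12, and (c) rests on the assumed 26. The mismatch itself needs only the Beta(1,5) prior, which Section 7.2.3 inherits and does not restate.

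The conflict between Section 7.2.1 and Sections 7.2.3 and 8.4 is separate and also real. It affects both Phase II toxicity tables. The plan must be corrected on both points.

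**What to change.** The sponsor should state which row was intended and amend the table so that each count and probability describe the same event:

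- if the printed probabilities stand, the matching counts are 2, 4, 5 and 6;
- if the printed counts stand, the matching probabilities are 0.87, 0.93, 0.90 and 0.88;
- if a different prior was used, it must be stated and reconciled with Section 7.1.3.

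The same amendment should restate the prior in Section 7.2.3, reconcile the sentence on early stopping in Section 7.2.1 with Sections 7.2.3 and 8.4, and say which looks apply under the amended feasibility enrolment. The choice between the rows is the sponsor's.

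The cost is a one-table correction and a few sentences, by amendment, with no new data. Changing the probability row leaves the operating characteristics as they are. Changing the count row raises the chance of reaching a boundary at an acceptable 10% rate by the amounts shown in the working.

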#### 7.2.4 Statistical Analyses.

Analyses of acute and late toxicity and fatigue will be completed within 1 year of completion of accrual. Time-to-event outcomes and long term longitudinal measurements of fatigue and neurocognitive function will be analyzed 2-3 years after completion of accrual. Descriptive analyses and subset analyses are likely. The purpose of these subset analyses is hypothesis generation. Subgroup analyses will likely describe time-to-event outcomes by histology (e.g., chordoma or chondrosarcoma) and extent of surgery (e.g., biopsy only, partial debulking, and maximal debulking). They will produce estimates of clinical outcomes, to aid in the design of future clinical trials.

Acute and Late Toxicity. All acute and late toxicities will be graded by CTCAE Version 4.0 and tabulated. Toxicity rates and 95% confidence intervals will be calculated. The maximum half-width of the 95% confidence interval is  $\pm 14\%$  based on 50 patients.

Time-to-Event Outcomes. Trials of chordomas and chondrosarcomas which combine proton with photon, have demonstrated 5-year progression-free survival rates (i.e., free of local failure) of 60-80%. We do not expect the 5-year PFS rate to be much different with protons. Progression-free and overall survival and time to local failure, will be estimated by the Kaplan-Meier method. Median and 5-year estimates and 95% confidence intervals will be calculated.

Fatigue (Brief Fatigue Inventory, BFI) & Neurocognitive function (FACT-Br) will be summarized by mean and standard deviation calculated and plotted over time. We will examine the plots for the expected worsening of function in the 6-12 months post-radiation and gradual improvement from 12-24 months. Pre- and post-treatment comparisons at a primary time point (e.g., at 24 months post-radiation when function should have recovered) will be evaluated by Student's paired t-test or nonparametric Wilcoxon signed ranks test. A general strategy to assess trends over time in longitudinal data is to employ linear mixed effects models, which can account for the impact of covariates such as anti-seizure medication and baseline performance status. The BFI can also be categorized as mild (1-3), moderate (4-6) and severe (7-10). The rates of patients in the severe category will be estimated at each time point. Of primary interest are the rates at 12 and 24 months post-treatment.

There are little data published on BFI and FACT-Br scores in chordoma patients treated with radiotherapy, but profound fatigue and neurocognitive impairment are known side effects of photon radiation. We anticipate that the rate of severe fatigue will be reduced with protons. We will perform one exploratory test to determine whether the 12 month rate of severe fatigue is lower than 50%.

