#### 7.1.2.2 Secondary Endpoints

Late toxicity is defined as any grade 3 or higher toxicity, considered probably or definitely related to radiation, observed later than 90 days from completion of therapy excluding cranial nerve palsies or nerve root symptoms as these may be due to the tumor itself or prior surgery. Late toxicities will be graded according to the CTCAE version 4.0. The time frame for late toxicity is open-ended and late toxicities have been known to occur a year or more after therapy. Follow-up for late toxicity will cease when a patient experiences disease progression, since 2nd line therapies may then be initiated.

Progression-free and overall survival are defined as the time from start of radiotherapy to first documented progression (local or distant event for PFS), death due to any cause or last patient contact alive. The local control rate (i.e., local progression only) may also be evaluated.

Fatigue will be scored by the Brief Fatigue Inventory (BFI), a validated instrument, which will be evaluated at the following time points: Pre-radiation, during treatment, at the inspection visit, and at approximately 3, 6, 9, 12 months post-radiation and then every 6 months for years 2 and 3, and yearly for year 4 and 5. It is expected that BFI score will increase (as fatigue worsens) in the first 6-12 months post-radiation and then the BFI score will decrease (as fatigue improves) at 12-24 months post-radiation.

Neurocognitive function will be assessed by the FACT-BR, which will be evaluated at preradiation, during treatment, at 3, 6, 9, 12 months post-radiation and then every 6 months.

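### Late toxicity is planned as a simple proportion within 1 year of completing accrual, with no risk period, no method for unequal follow-up and no later analysis named

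*Combined protocol and SAP*

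**What the plan says.** All of this is in the combined protocol and SAP.

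- **Timing and estimator (7.2.4).** "Analyses of acute and late toxicity and fatigue will be completed within 1 year of completion of accrual". Toxicities are graded and tabulated, and "Toxicity rates and 95% confidence intervals will be calculated". The stated maximum half-width is ±14% on 50 patients.
- **Later analysis (7.2.4).** "Time-to-event outcomes and long term longitudinal measurements of fatigue and neurocognitive function will be analyzed 2-3 years after completion of accrual". Fatigue is therefore named for both the early and the later analysis. Late toxicity is named only for the early one.
- **Methods that allow for censoring (7.2.4).** "Progression-free and overall survival and time to local failure, will be estimated by the Kaplan-Meier method". Late toxicity is not on that list.
- **Endpoint definition (7.1.2.2, carried into Phase II by 7.2.2).** Late toxicity is grade 3 or higher, probably or definitely related to radiation, and "observed later than 90 days from completion of therapy". The time frame is open-ended because "late toxicities have been known to occur a year or more after therapy". Also, "Follow-up for late toxicity will cease when a patient experiences disease progression".
- **Data collection (6.0 and 6.1).** Toxicity is assessed at follow-up visits through year 5.
- **Feasibility analysis (7.1.4).** "All toxicities observed later than 90 days from start of therapy will be graded by the CTCAE version 4.0 and tabulated". This is again a tabulation with no time point.

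**The concern.** A simple proportion suits acute toxicity, where every patient has the same 90-day window. Late toxicity has staggered entry, one calendar cut and no fixed horizon. A patient followed for 7 months and one followed for 58 months then count equally in the denominator. The result is the risk over whatever mix of follow-up exists at the cut, so it changes with accrual speed and cut date. It cannot be read as a 2-year or 5-year risk, or compared with another series.

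Section 7.2.1 gives characterizing toxicity rates as a purpose of Phase II, and section 2 lists late complications as an objective. Toxicity data collected after the early cut have no stated analysis.

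**Working it through.** **1. The plan's own figure.** 1.96 × √(0.5 × 0.5 / 50) = 13.9%, which rounds to ±14%. The figure is right for a binomial proportion with all 50 patients fully observed.

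**2. Follow-up at the cut.** Inputs from the documents:

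- 12 patients per year, with a 2-month pause after the first 12 (7.3)
- up to 15 per year (3.3)
- a 9-week course (4.6), i.e. 63 days = 2.1 months
- a late window opening 90 days after completion (7.1.2.2), i.e. about 5.0 months from start

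Assumed: even entry, radiation starting at entry, no dropout, and a 6-month cut as an example of an earlier permitted date.

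At 12 per year, entries fall at months 0 to 11 and then 14 to 51. With a cut 12 months after the last entry (month 63):

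- The first patient has 63 − 5.0 = 58.0 months in the late window and the last has 12 − 5.0 = 7.0. The median is about 31.
- Under 24 months after radiation means entry after month 63 − 24 − 2.1 = 36.9. Entries at months 37 to 51 qualify, which is 15 patients.
- One patient reaches 60 months after radiation.

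| Accrual, cut | Late-window follow-up (months) | Under 24 months post-radiation |
|---|---|---|
| 12/year, 12 months | 7-58 | 15 of 50 |
| 12/year, 6 months | 1-52 | 21 of 50 |
| 15/year, 12 months | 7-48 | 18 of 50 |
| 15/year, 6 months | 1-42 | 26 of 50 |

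Sections 7.1.4 and 7.3 enlarge the feasibility stage, and 7.1.4 refers to 26 patients. At 12 per year with a 12-month cut, that gives a median of 33 months if the total stays at 50, or 38 if 38 patients are still added (total 64). In both cases 15 patients have under 24 months, i.e. 30% or 23%.

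**3. Size of the effect (illustration only).** Take a constant late-toxicity hazard λ = −ln(1 − R)/60 per month. Follow-up stops at hazard μ = −ln(PFS5)/60. R is 5% or 10%, borrowed from section 1.1, where the figure is specific neither to grade 3+ nor to a time point. PFS5 is 60% or 80% (7.2.4). With w = 5.03 months to window opening, incidence by t months from start is

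I(t) = exp(−μw) × λ/(λ+μ) × [1 − exp(−(λ+μ)(t − w))].

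The expected crude rate is the mean of I(c) over patients, where c is each patient's time from start to the cut.

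Example: R = 10%, PFS5 = 80%, 12 per year, 12-month cut. Then λ = 0.001756 and μ = 0.003719.

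- I(24) = 0.9815 × 0.3207 × 0.0987 = 3.1%
- I(60) = 0.9815 × 0.3207 × 0.2599 = 8.2%
- Crude rate = 5.0%

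In patients per 50, the crude rate is 0.9 above the 2-year value and 1.6 below the 5-year value.

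Over R 5-10%, PFS5 60-80%, 12 or 15 per year and a cut at 6 or 12 months, the crude rate is 0.41-0.63 of the 5-year incidence and 1.06-1.61 times the 2-year incidence. The differences are 0.05-0.93 patients above the 2-year value and 0.7-2.4 below the 5-year value. Counting time from end of radiation or from window opening widens the 5-year shortfall to 0.6-3.0 patients. Counted from end of radiation, the 2-year difference runs from −0.05 to +0.77. For comparison, the exact 95% interval for 3/50 is 1.3-16.5%.

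**4. Separate check: the windows.**

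- Acute: within 90 days of start (3.4.1, 7.1.2.1, 7.1.4), or through day 90 after treatment (8.1).
- Late: from 90 days after completion (7.1.2.2), or from 90 days after start (7.1.4).

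Phase II inherits 7.1.2.1 and 7.1.2.2 through 7.2.2. With a 63-day course, acute ends on day 90 and late begins after day 63 + 90 = 153. Grade 3+ events on about days 91-153 count as neither.

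**The case against.** The case for leaving the plan alone has real weight.

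- **Silence is not prohibition.** A reader might infer that late toxicity will be analysed only once and never updated. The documents do not say so. Completing an analysis within a year does not bar another, and fatigue, in the same sentence, gets a second one. What stands is that no later late-toxicity analysis is named.
- **The effect is small.** Against 2-year incidence, where the fix can be reasonably precise, the difference is about 1 patient in 50 or less, and its direction depends on the time origin. The 5-year shortfall of 1-3 patients is within sampling error. This stands, and it limits the weight of the point.
- **The illustration rests on assumptions.** Constant hazard, even accrual and the 6-month cut are not in the documents, and the 5-10% risk is borrowed. Conceded. The unequal follow-up itself needs only the plan's accrual and timing figures plus even entry.
- **Stopping at progression is not settled.** Section 7.1.2.2 ends late-toxicity follow-up there, while 3.4.1 promises every effort to follow off-study patients for toxicity. The illustration assumes 7.1.2.2 governs.
- **The ±14% is a maximum.** At a 10% rate the simple half-width is 8.3% with 50 patients and 10.6% with 31. The figure is not wrong, but it describes a different quantity from a time-specific risk.
- **A tabulated rate with its follow-up range would go a long way.** True for the early table. It still would not give a risk at a stated time.
- **The window gap depends on which sections are paired.** Pairing 8.1 with 7.1.2.2, or 7.1.2.1 with 7.1.4, closes it. The conflict remains, and the pair carried into Phase II leaves the gap.

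**Conclusion.** The concern holds as a defect in how the late-toxicity rate is defined. Following section 7.2.4 gives a proportion with no risk period, pooling patients with about 7 to 58 months in the late window (12 per year, 2-month pause, 12-month cut), 15 of 50 of them under 24 months after radiation. An earlier cut or faster accrual shortens follow-up further.

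A reader might go further and conclude that the plan will seriously understate late harm or compromise a decision. The documents do not support that. Late toxicity is secondary and descriptive, with no test and no stopping rule. Under assumed constant hazards and a 5-10% five-year risk, the discrepancy is about 1 patient in 50 or less at two years and about 1-3 at five. The change should be made for interpretability; it does not threaten the trial's conclusions.

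The window conflict is a separate inconsistency. It needs no assumed hazard, but the exact days depend on course length.

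**What to change.** - **Early table.** Keep the acute analysis and a descriptive late-toxicity table within 1 year of completing accrual. Report the follow-up range with it.
- **Later analysis.** In the 2-3 year analysis already planned, add cumulative incidence of first grade 3+ late toxicity at named times, for example 1 and 2 years, with 5 years flagged as imprecise. Give 95% confidence intervals and numbers at risk. Treat death as a competing event, and progression too if follow-up stops there.
- **Precision statement.** Say that ±14% applies to a simple proportion with all 50 patients observed, and so does not describe the time-specific late-toxicity estimates.
- **Reconciliation.** Make the acute and late windows contiguous across 3.4.1, 7.1.2.1, 7.1.2.2, 7.1.4 and 8.1. Reconcile 3.4.1 with 7.1.2.2 on toxicity follow-up after progression.

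**Cost.** SAP wording and one standard analysis of data already scheduled through year 5. No early safety information is lost, but the final late-toxicity estimate comes 1-2 years after the early table.

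**Gain.** In the same illustration, about 36-45 patients are event-free and under follow-up at 24 months after radiation in the 2-3 year analysis, against 18-31 at a cut 6-12 months after accrual. The 5-year value would still rest on about 2-17 patients.

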### **3.4** Early Withdrawal of Subjects

### 3.4.1 When and How to Withdraw Subjects

- Recurrent or Progressive Disease: Subjects who have clinical or radiologic evidence of recurrent disease will undergo an evaluation to document the nature of the abnormality. If recurrent or progressive cancer is diagnosed, the subject will be considered off study at that time.
- PI Decision: Subjects may be withdrawn at any time during the study if the PI believes it is in the subject's best interest. In this event, the reasons for withdrawal will be documented.
- Subject Participation: Refusal to continue treatment, follow-up, comply with the protocol or withdrawal of consent. In this event, the reasons for withdrawal will be documented.
- Adverse Event (including intercurrent illness, unacceptable toxicity).

Once the subject has discontinued treatment, the primary reason for discontinuing treatment must be clearly documented in the subject's records and on the CRF. The investigator will assess each subject for response at the time of withdrawal.

Every effort will be made to follow all subjects off study for toxicity and survival unless patient withdraws consent. If subjects withdraw from the study at any time, we will ask for his/her written permission to continue to access medical records for overall survival. Acute toxicities will be assessed for 90 days from the first date of treatment. Survival will be followed for a minimum of 5 years.

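### Section 7.2.4 plans 5-year Kaplan-Meier estimates but schedules time-to-event analysis only 2-3 years after accrual, so part of the 5-year follow-up enters no planned analysis

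*Combined protocol and SAP*

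**What the plan says.** All of the analysis text is in Section 7.2.4. On timing, time-to-event outcomes "will be analyzed 2-3 years after completion of accrual". On method, "Progression-free and overall survival and time to local failure, will be estimated by the Kaplan-Meier method". On the quantities reported, "Median and 5-year estimates and 95% confidence intervals will be calculated". The section cites 60-80% as the 5-year PFS range seen when protons were combined with photons, and expects a similar figure here.

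Follow-up is longer than that timing. Section 3.4.1 states: "Survival will be followed for a minimum of 5 years". Section 6.1 schedules visits and MRI every 3 months for two years, every 6 months in year 3, and yearly in years 4 and 5.

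Section 7.3 gives the accrual plan: "We estimate that the first 12 patients will be enrolled in 1 year", "Then the study will be suspended for patient observation for 2 months", and, if the feasibility study is acceptable, "then an additional 38 patients will be enrolled for a study total of 50 patients". It adds: "With an accrual of 12 patients per year, the study should be actively enrolling for 4 years". Section 3.3 gives a slightly wider rate of 12-15 per year.

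No further time-to-event analysis, interim or final, is described anywhere.

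**The concern.** The reporting horizon is 5 years, and the data to support it are scheduled for every patient who stays in follow-up. The analysis is placed when the last patients enrolled have only 2 or 3 years of follow-up. The part of the curve near 5 years then rests on the earliest enrolled patients, and later patients' remaining follow-up feeds no planned analysis.

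What is at stake is the width of the interval around the 5-year rates. The histology and extent-of-surgery subgroups, which Section 7.2.4 wants as input to future trial designs, would start from smaller numbers still. Late events matter in this disease: Section 1.1 notes relapse ten years or more after surgery.

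**Working it through.** **The plan's own figures.** 12 per year for 4 years gives 12 × 4 = 48, close to the planned 50. The ±14% half-width that Section 7.2.4 gives for toxicity rates also reproduces: 1.96 × √(0.25/50) = 13.9%.

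**Potential follow-up.** Patient i enters at i/12 years, plus 2/12 for i > 12. Accrual ends at 50/12 + 2/12 = 4.33 years. With the analysis L years later, a patient has 5 years of potential follow-up if entry is no later than 4.33 + L − 5.

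- L = 2: entry by 1.33 years. Patient 14 enters at 14/12 + 2/12 = 1.33, so **14 of 50**.
- L = 3: entry by 2.33 years. Patient 26 enters at 26/12 + 2/12 = 2.33, so **26 of 50**.

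Sensitivity (L = 2, L = 3):

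- no pause or a 90-day pause: 14, 26
- 12.5 per year over exactly 4 years: 12, 25
- pause after 26 patients (the amended feasibility total in Section 7.1.4): 16, 26
- 15 per year: 7, 20
- 8 per year (an assumed slow case): 26, 34

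**Still at risk at 5 years.** Multiply by the 5-year PFS rate, assuming no dropout. At L = 2: 14 × 0.6 = 8.4 to 14 × 0.8 = 11.2. At L = 3: 26 × 0.6 = 15.6 to 26 × 0.8 = 20.8. With full follow-up: 30 to 40.

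**Precision.** Assume a constant hazard λ = −ln S(5)/5 and administrative censoring only. With n(u) the number of patients whose potential follow-up reaches u, the large-sample Greenwood form is

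half-width = 1.96 × S(5) × √( ∫₀⁵ λ / [n(u) S(u)] du ).

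With full follow-up this reduces to 1.96 × √(S(1−S)/50). Simulating 3,000 trials per case gives nearly the same values (in brackets). Half-widths in percentage points:

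| 5-year PFS | L = 2 | L = 3 | Full follow-up |
|---|---|---|---|
| 60% | 17.0 (17.2) | 14.8 (15.1) | 13.6 (13.3) |
| 70% | 15.8 (15.7) | 13.8 (13.6) | 12.7 (12.6) |
| 80% | 13.7 (13.4) | 12.0 (11.9) | 11.1 (11.1) |

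The simulated mean estimates were within 0.2 points of the true 60%, 70% and 80%, so there is no visible bias.

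**Follow-up left out.** Years 4 and 5 (months 36-60) hold 50 × 2 = 100 potential patient-years. Summing each patient's share before the cut-off gives 51 at L = 2 and 75 at L = 3, so **49% or 25%** is left out. Over the whole 0-5 year span, 78% or 90% is captured.

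**The case against.** The case for leaving the plan alone is substantial. Kaplan-Meier is built for staggered entry, and all 50 patients contribute to at least the first 2 or 3 years of the curve. At the 3-year limit of the plan's own window the loss is only about 1 point of half-width; with 50 patients the interval is wide whatever the timing. PFS and OS are secondary, and no test, stopping rule or sample-size calculation uses them. All of this stands, and it limits the point to a minor one.

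Several stronger readings are tempting, but the documents do not support them.

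- *That the 5-year rate cannot be estimated or is biased.* Under non-informative censoring it can be estimated and is essentially unbiased.
- *That follow-up in years 4-5 is mostly never analysed.* At least half of it falls before the cut-off (51% or 75%). Potential follow-up of 4 years or more is available for 26 or 38 patients.
- *That the 5-year figure comes mainly from patients treated before the amendment.* Section 7.1.4 gives 26 feasibility patients with 17 after the modification, hence 26 − 17 = 9 before it. If those 9 are counted in the 50 and enrolled first, they are 9 of 14 at the 2-year cut-off but only 9 of 26 at the 3-year cut-off. Later patients also shape the earlier part of the curve.
- *That 5-year survival is the main result.* Section 7.2.1 gives the purpose as toxicity and fatigue, with PFS estimated in addition.
- *That a later analysis is ruled out.* The plan does not call the 2-3-year analysis final. An update is simply not planned.

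Making 2- or 3-year rates the main estimates instead would be a matter of preference. It would also remove the comparison with the only benchmark the plan cites, which is a 5-year one.

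**Conclusion.** The mismatch is real and minor. The plan promises 5-year estimates, schedules the follow-up needed for them, and places its only described time-to-event analysis before that follow-up is complete. The cost is about 2.5-4 points of 95% half-width at the 2-year cut-off and about 1-2 points at the 3-year cut-off, with roughly 49% or 25% of potential year 4-5 follow-up outside any planned analysis. The subgroup curves, being smaller, would be less precise still.

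These sizes rest on accrual at 12 per year, a constant hazard, 5-year PFS of 60-80% and no dropout. Faster accrual or dropout lowers the numbers at risk, and slower accrual raises them. A hazard rising over time (Weibull shape 1.5, assumed) widens the 2-year half-width at 70% PFS to about 17 points.

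**What to change.** In Section 7.2.4:

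- Keep the 2-3-year analysis with its 5-year estimate, report the numbers at risk alongside the curves (overall and by subgroup), and label that estimate provisional.
- Add a final Kaplan-Meier analysis of PFS, OS and time to local failure once the last patient has completed the scheduled 5-year visit.

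The cost is a few lines of text and one repeat analysis. No extra patients, visits or scans are needed, because Sections 3.4.1 and 6.1 already schedule the follow-up. The downside is that the final figure arrives 2-3 years after the provisional one (5 − 3 to 5 − 2 years, plus a few weeks because visits are counted from the last treatment).
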